6.3.1 Datasets to be analysed, analysis populations

For the primary analysis we will use the available case population of primary school students which will be analysed according to the intention-to-treat principles.

6.3.1.1 Primary Analysis

Module 1: RANAS and well-being survey: The data will be summarized using descriptive statistics. Associations of RANAS behavioural factors with good handwashing practices and students' well-being with the other outcome variables from RANAS behavioural factors will be estimated using random effect linear regression modelling and random effect logistic regression modelling. Missing data will clearly be reported but not imputed.

Module 2: Structured handwashing observations: To quantify the intervention effect logistic regression with binomial distribution with random intercepts for schools models will be applied.

Module 3: Microbiological analysis of hand rinse samples: For investigating factors associated to *E.coli* and total coliform prevalence on primary school students' hands, random effect linear regression models will be applied.

Module 4: Diary approach for hygiene-related health outcomes and absenteeism: The rates of hygiene-related absenteeism will be calculated separately for each health outcome per school. To quantify the intervention effect on hygiene-related health outcomes and absenteeism, random effect linear regression modelling will be used.

Module 5: Personal, physical and social contextual factor survey: The independent and joint association of personal, physical and social contextual characteristics with handwashing behaviour, and well-being (total score and domain-specific scores) will be analysed in the context of multivariate regression models that apply a variable-selection procedure that takes interactions into consideration to not miss those factors where the association depends on the presence of one or more additional variables. To assess personal profiles consisting of a combination of factors, a clustering approach for factors with a statistically significant association with handwashing or well-being will be applied.

Modules 6 and 7, FGDs and KIIs: FGDs and KIIs will be audio recorded, transcribed, and translated if necessary for further analysis. The local perception of the success and sustainability of the H4H intervention will be analysed using the framework method with the software MaxQDA (VERBI Software, Marburg, Germany) or NVivo (QSR International, Melbourne, Australia) (48).

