Module 4 follows the sample size calculation of the cRCT design, hence 50 students from each of the 24 schools will be monitored. For module 5 which is only restricted to students from Palestine, the same sampling plan of the cRCT will be used, and the sample size will be the one foreseen to fulfil the main study objectives. For Module 6, 10 FGDs (including students) and 5 FGDs (including teachers) will be administered and for Module 7, 10-20 interviews.

[figure not shown]

Figure 2: Consort flow diagram of the schools selection for the H4H cRCT in Nigeria

The methods to achieve the different objectives of this project are summarized in Table 1. These modules will include qualitative and quantitative data approaches in order to enable a triangulation of the overall project results. The following modules will be used in the cRCT and the overall project: (i) Module 1: Combined RANAS and well-being survey, (ii) Module 2: Structured handwashing observations, (iii) Module 3: Microbiological analysis of hand rinse samples, (iv) Module 4: Diary approach for health outcomes and absenteeism, (v) Module 5: personal, physical and social contextual factors survey (vi) Module 6: Focus Group Discussions (FGDs) and (vii) Module 7: Key informant interviews (KIIs).

Table 1: Overview of different project modules and analysis by objective

Module	Objective	Analysis
Module 1: Combined RANAS and well-being survey	
PO: Evaluate the effects of the H4H MCI on hand hygiene of primary school students in Nigeria and Palestine
 
SO1: Evaluate the effects of the H4H MCI on the well-being of primary school students in Nigeria and Palestine
 
SO2: Assess the effect of the H4H MCI on hygiene-related RANAS behavioural factors of primary school students
	
 - Descriptive statistics and multiple random effect regression models
Module 2: Structured handwashing observations	PO: Evaluate the effects of the H4H MCI on hand hygiene of primary school students in Nigeria and Palestine	
 - Descriptive statistics, multiple linear regression models and logistic regression models
Module 3: Microbiological analysis of hand rinse samples	PO: Evaluate the effects of the H4H MCI on hand hygiene of primary school students in Nigeria and Palestine	
 - Analysis of E. coli and total coliforms - Descriptive statistics, multiple linear regression models

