4.2 Secondary endpoints

The most important secondary endpoints are:

- A) Good handwashing practice defined as students who wash their hands with water and soap after using the toilet assessed by structured handwashing observation
- B) Self-reported handwashing practice at the two critical events (before eating and after using the toilet) including occurrence, frequency and technique of handwashing behaviour will be assessed using the survey on a Likert scale ranging from almost never to almost always.
- C) The well-being of the students will be assessed using the KINDL tool (Ravens-Sieberer and Bullinger 1998).
- D) The log-transformed number of total coliforms and E.coli CFUs per hand before handwashing.
- E) Hygiene-related health outcomes and absenteeism. The health outcomes will be reassessed with local experts to assure feasibility before the start of the intervention.

Covariates are assessed with RANAS variables as exposure variables and good handwashing practice as outcome variable. Covariates for estimating the total effect of RANAS on good

handwashing practice are age, education, sex, socio-economic status, handwashing practices, and the water infrastructure of the schools.

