6.1.2 Secondary hypotheses

Depending on the secondary objective, different secondary hypotheses were formed:

$H_{1,1}$ = There is a difference in well-being between the intervention and control groups of primary school students in Nigeria and Palestine.

$H_{0,1}$ = There is no difference in well-being between the intervention and control groups of primary school students in Nigeria and Palestine.

$H_{1,2}$ = There is a difference between hygiene-related RANAS variables between the intervention and control groups of primary school students in Nigeria and Palestine.

$H_{0,2}$ = There is no difference between hygiene-related RANAS variables between the intervention and control groups of primary school students in Nigeria and Palestine.

$H_{1,3}$ = There is association between personal, physical and social contextual factors and hand hygiene and the well-being of primary school students in Palestine.

$H_{0,3}$ = There is no association between personal, physical and social contextual factors and hand hygiene and the well-being of primary school students in Palestine.

$H_{1,e}$ = There is a difference in hygiene-related health outcomes and absenteeism between the intervention and control groups of primary school students in Nigeria and Palestine.

$H_{0,e}$ = There is no difference in hygiene-related health outcomes and absenteeism between the intervention and control groups of primary school students in Nigeria and Palestine.

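### Modules 1 and 3 have only factor-association models, so no arm model is stated for well-being, self-reported handwashing, CFU counts or the RANAS factors, although Table 1 shows that one was intended

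*Combined protocol and SAP*

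**What the plan says.** **What is to be shown.** Section 6.1.2 words two secondary hypotheses as comparisons of arms: "There is a difference in well-being between the intervention and control groups of primary school students in Nigeria and Palestine" and "There is a difference between hygiene-related RANAS variables between the intervention and control groups". Section 3.1.3 asks, in RQ 1.1 under secondary objective 1 and in RQ 2.1, whether well-being and the RANAS factors change because of, or in association with, the intervention. Table 1 in Section 4 gives Module 1 the objective "SO1: Evaluate the effects of the H4H MCI on the well-being of primary school students in Nigeria and Palestine", with a matching one for RANAS factors, and assigns Module 3 to the primary objective. Section 4.2 lists self-reported handwashing (B), KINDL well-being (C) and, as D, "The log-transformed number of total coliforms and E.coli CFUs per hand before handwashing".

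**What is to be fitted.** Section 6.3.1.1 says for Module 1: "Associations of RANAS behavioural factors with good handwashing practices", and of well-being with the RANAS variables, by random effect linear and logistic regression. The next relevant entry begins "Module 3: Microbiological analysis of hand rinse samples: For investigating factors associated to" and names E. coli and total coliform prevalence, by random effect linear regression. In the same section, Modules 2 and 4 are each introduced as estimating the effect of the intervention. Section 4.2 also treats the RANAS variables as exposures, with handwashing as the outcome.

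**The concern.** The hypotheses ask whether the arms differ. The models written for Modules 1 and 3 ask whether one measured characteristic goes with another. An analyst who followed Section 6.3.1.1 literally would report observational associations for these outcomes and make no use of the randomisation.

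An analyst who supplied the missing arm model later would have to choose the time point (baseline, three months and endline are all collected), the covariates, the treatment of the baseline value and the scale. Those choices would be made with the data in view. The baseline value of each outcome is collected in Modules 1 to 3, yet no main model uses it.

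**Working it through.** **1. Where arm is named as a predictor.**

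- Synopsis and Section 6.3: intervention as the only predictor, school as random effect. The sentence belongs to the logistic model for handwashing before eating.
- Section 6.3.1.1, Modules 2 and 4: intervention effect named.
- Section 6.3.1.1, Modules 1 and 3: arm not named.
- Section 6.3.1.2: adds covariates to models already defined and introduces no new comparison.
- Table 1: model family only, with no arm term, time point or baseline handling.

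Endpoints B, C and D of Section 4.2, and the RANAS hypothesis of Section 6.1.2, are left without a stated arm model.

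**2. The plan's own figure.** The only sample size is for handwashing before eating (20% against 45%, ICC 0.2, 50 students per school, 80% power). Two-sided 5% testing is taken here. An individually randomised comparison needs 54 per arm. The design effect is 1 + 49 × 0.2 = 10.8, and 54 × 10.8 / 50 = 11.7, so 12 schools, or 13 with the usual extra cluster. A beta-binomial simulation gives 78.9% power at 12 schools and 81.6% at 13. The stated 13 per arm therefore reproduces, and this point does not affect it.

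**3. Do the association models test the arm hypotheses?** Illustration under assumed values: 13 schools per arm, 25 students per school (the Module 1 number), ICC 0.2, and 200 simulated trials per scenario. The association model regresses well-being on a RANAS score. The arm model regresses the RANAS score on arm. Both have a school random intercept.

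- No arm effect, RANAS–well-being association 0.3: association model significant in 100%, arm model in 5%.
- Arm effect of 0.6 SD on RANAS, no association: association model significant in 9%, arm model in 94%.

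The simulation error on the 9% is √(0.09 × 0.91 / 200) = 0.020, about 2 percentage points. The fitting routine gave a convergence warning, so the figures are approximate. The contrast is far larger than either limitation: each model is blind to what the other tests.

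**4. What the baseline value could add.** With r the correlation between baseline and endline school means, adjustment multiplies the variance of the arm effect by at best 1 − r²:

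- r = 0.3: 1 − 0.09 = 0.91, a fall of 9%
- r = 0.5: 1 − 0.25 = 0.75, a fall of 25%
- r = 0.7: 1 − 0.49 = 0.51, a fall of 49%

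The documents give no r. A student-level correlation does not fix it. With 25 students and ICC 0.2 (borrowed from the primary endpoint), the variance of a school mean is 0.2 + 0.8/25 = 0.232. The school part is 0.2/0.232 = 0.86 and the student part 0.14, so r ≈ 0.86 × school-level correlation + 0.14 × within-school student correlation. With a student correlation of 0.5:

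- school-level correlation 0.3: r ≈ 0.33, a fall of about 11%
- school-level correlation 0.8: r ≈ 0.76, a fall of about 58%

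**5. Scale of the CFU outcome.** Section 4, Module 3, sets the detection limits at 1 and 500 CFU per plate, divided by the filtrate volume and multiplied by 350 mL. At the planned 100 mL these are 1/100 × 350 = 3.5 and 500/100 × 350 = 1,750 CFU, or 0.54 to 3.24 on the log10 scale. Values outside that range are censored, and the analysis text does not say how they enter the model.

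**The case against.** The best defence is that the arm comparison is implied. Table 1 pairs the effect objectives with random effect regression for Module 1 and puts Module 3 under the primary objective. RQ 2.1 itself uses the language of association for the intervention, so the factors in Module 3 could include arm. The intervention-only rule in Section 6.3 could be stretched over everything under the heading Primary Analysis. This stands as evidence of intent. It does not supply a model: the rule in Section 6.3 is attached to a binary outcome and cannot be carried unchanged to a KINDL score or log10 CFU, and neither time point nor baseline handling follows from any of these passages.

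It can also be said that Section 6.3.1.2 would admit a baseline value as a known confounder or an imbalanced variable. It could, but only conditionally and in a secondary analysis. Leaving it out of the main model is a loss of efficiency, not an error.

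Four stronger readings are tempting and are not supported:

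- That the between-arm tests were dropped. Table 1 and the research questions show otherwise.
- That RANAS factors are a secondary endpoint, or that CFU has a hypothesis of its own. RANAS factors appear as an objective and a hypothesis but not in Section 4.2. CFU is an endpoint without a separate entry in Section 6.1.2.
- That a linear model is wrong for coliform prevalence. Section 4 says the counts are log10 transformed for analysis, which suits a linear model. Prevalence is loose wording.
- That the variance reduction can be converted into a number of schools saved. The 13 per arm was derived for a different, binary endpoint, and no size was derived for these outcomes.

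**Conclusion.** The point holds as a gap in specification for non-primary outcomes. Section 6.3.1.1 states factor-association models where the hypotheses, research questions and Table 1 call for an intervention effect. KINDL well-being, self-reported handwashing, log10 CFU per hand and the RANAS factors have no stated arm model. The primary analysis and the sample size are untouched.

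The main conclusion rests on the text alone. The simulation percentages depend on the assumed ICC, association and effect size, and only illustrate that the models answer different questions. The 9%, 25% and 49% are also illustrative: they need r to be the correlation of school means, the same students to be measured at baseline and endline (which the unique IDs and follow-up lists imply), and a baseline slope close to the between-school one.

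**What to change.** In Section 6.3.1.1, for the KINDL score, self-reported handwashing, log10 CFU per hand and each RANAS factor, state that the intervention effect is estimated at endline by a mixed model with:

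- arm as predictor;
- the student's baseline value of the same outcome;
- the variables used to stratify or constrain the randomisation, named in the plan, and country if the two countries are pooled;
- a random intercept for school.

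Report the adjusted arm difference with a 95% CI. For the Likert self-report, use a model suited to its scale. For Module 3, replace prevalence by log10 CFU per hand, state how values at or beyond the detection limits are handled, and align Table 1, which omits the random effect. Keep the factor–outcome associations, which serve RQ 2.2, but label them exploratory, together with the set of RANAS-factor comparisons.

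The cost is wording. The outcomes are already collected at baseline and endline, and no sample size changes. The text should be settled before the endline data are examined.

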6.3.1.2 Secondary Analyses

In a secondary analysis the models will be adjusted for known confounder and additional predictors imbalanced at baseline.

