
Measurements and Procedures
	
Different methods across modules will be used to achieve the objectives of this project. These modules will include qualitative and quantitative data approaches in order to enable a triangulation of the overall project results. The following modules will be used in the cRCT and the overall project: (i) Module 1: A combined RANAS and wellbeing survey, (ii) Module 2: Structured handwashing observations, (iii) Module 3: Microbiological analysis of hand rinse samples, (iv) Module 4: Diary approach for pre-defined health outcomes and absenteeism incidence, (v) Module 5: personal, physical, and social contextual factor survey, (vi) Module 6:FGDs and (vii) Module 7: Key informant interviews (KII).
 
Endpoints of Modules 1-3 will be assessed at baseline, at follow-up and endline of the cRCT. Module 4 will be used to collect data longitudinally over the course of 12 months. Module 5 will be assessed at baseline and only in Palestine, Module 6 and 7 will be used in the middle of the intervention phase in the intervention groups.

Number of Participants with Rationale (if no Power Analysis conducted)
	
The sample size calculation yielded that 13 schools are needed per arm with 50 students per school. With political instability and other factors which might lead to a loss of follow-up, we have 7 schools as backup schools. This will lead to 26 schools in total with a total number of 1300 students. The number of students participating in different modules will differ due to the capacity limitation of assessing the 50 students included in each school. For module 1, only 25 students of the 50 students included in the study in each school. For module 2, the 50 students included in the study in each school will be targeted for assessment using this module. For Module 3, 12 students out of the 25 randomly selected students to be targeted with RANAS and well-being survey will be targeted for assessment using this module.

	
Module 4 follows the sample size calculation of the cRCT design, hence 50 students from each of the 26 schools will be monitored. For Module 5, all students in the included classes in each school in Palestine will be delivered a survey to be self-reported by their parents. For Module 6, 10 FGDs (including students) and 5 FGDs (including teachers) will be administered and for Module 7, 10-20 interviews.

Study Duration	14 months

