Study Schedule	
For Nigeria: May 2023 of First-Participant-In July 2024 of Last-Participant-Out
 
For Palestine: March 2023 of First-Participant-In May 2024 of Last-Participant-Out

Investigator(s)	
[name]. [name] Swiss Tropical and Public Health Institute [name] [contact] [contact]
 
PhD candidate (research assistant) under supervision of [name]. [name]: [name] Swiss Tropical and Public Health Institute [name], Switzerland [contact]
 
[name] Terre des hommes Nigeria [name] [contact], [name] [contact]
 
[name] Project coordinator Cesvi Palestine [name] [name] [contact]
 
[name] Junior Programme Officer Skat Foundation [name] [contact] [contact]

Study Centre(s)	Nigeria and Palestine
Statistical Analysis incl. Power Analysis	The number of clusters (schools) and students per school were calculated using the software R with a power simulation of 80% developed by [name]. The Intraclass Correlation Coefficient (ICC) was assumed at 0.2. The simulation assumed a prevalence of handwashing occurrence before eating during the time of observation (3 hours) taking place over one day of 20% in control vs 45% in intervention schools after 1 year from the

	
baseline. Based on this assumption, 13 schools are needed per arm with 50 students per school.
 
The baseline data will be reported descriptively. The imbalance at baseline between trial arms will be assessed in terms of clinical importance rather than in terms of statistical significance. The intervention effect will be estimated with logistic mixed effect regression to adjust for potential correlation within schools. For the primary analysis, the model will include only the outcome (handwashing occurrence before eating during the time of observation (3 hours) taking place over one day and assessed at the endline) and the intervention as a predictor and school as a random effect. Further analyses will include known confounders and variables imbalanced at baseline. All analyses will use the available case population. No imputation of missing data will be done because loss to follow-up is usually small to moderate in school-based studies.

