6 STATISTICS

6.1 Hypothesis

6.1.1 Primary hypothesis

The primary hypothesis stems from the research question: Does the H4H MCI make a difference in the hand hygiene of primary school students in Nigeria and Palestine?

$H_{1,1}$ = There is a difference in hand hygiene between the intervention and control groups of primary school students in Nigeria and Palestine.

$H_{0,1}$ = There is no difference in hand hygiene between the intervention and control groups of primary school students in Nigeria and Palestine.

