6.2 Determination of sample size

The number of clusters (schools) and students per school was assessed by simulations using the software R aiming for a power of 80% at the 95% confidence level. The Intraclass Correlation Coefficient (ICC) was assumed at 0.2. The simulation assumed a prevalence of handwashing occurrence before eating during the time of observation (3 hours) taking place over one day of 20% in control vs 45% in intervention schools after 1 year from the baseline. Based on this assumption, 13 schools are needed per arm with 50 students per school. However, the number of students assessed for different modules will differ due to the capacity limitation of assessing the 50 students included in each school.

For Module 1, only 25 students randomly selected out of the 50 students randomly selected from the classes included in the intervention in each school will be targeted. For Modules 2 and 4 the 50

students randomly selected from the one or two classes included in the intervention in each school will be targeted. For Module 3 only 12 students randomly selected out of the 25 students involved in module 1 in each school will be targeted. For Module 5, all students in the the classes included in the intervention in each school will be invited to participate by delivering a survey to be reported by one of their parents. For Module 6, 10 gender-separated FGDs will take place in the included schools in the intervention arm; 5 FGDs for each gender. In addition, 5 FGDs targeting teachers will be conducted. For Module 7, 10-20 interviews will be conducted.

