6.3 Description of statistical methods

Baseline characteristics will be summarized using descriptive statistics. The difference in the observed proportion of washing hands before eating between two study arms at follow-up will be investigated using logistic mixed effect regression to adjust for potential correlation within schools. In the primary analysis only the intervention will be included as predictor and school as a random effect.

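### The secondary adjusted analysis has no fixed covariate list and lets observed baseline imbalance decide part of what enters the intervention-effect model

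*Combined protocol and SAP*

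**What the plan says.** The primary model is fixed and unadjusted. Section 6.3 states: "In the primary analysis only the intervention will be included as predictor and school as a random effect".

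The adjusted model is secondary. Section 6.3.1.2 states: "In a secondary analysis the models will be adjusted for known confounder and additional predictors imbalanced at baseline". The Synopsis (Statistical Analysis) has nearly the same rule: "Further analyses will include known confounders and variables imbalanced at baseline". The two differ in one word: section 6.3.1.2 speaks of predictors, the Synopsis of variables. On how imbalance is judged, the Synopsis says: "The imbalance at baseline between trial arms will be assessed in terms of clinical importance rather than in terms of statistical significance". No numerical threshold is given.

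No confounder is named for the intervention-effect model. The only explicit list is in section 4.2, in a sentence that ends "handwashing practice are age, education, sex, socio-economic status, handwashing practices, and the water infrastructure of the schools". That sentence concerns the effect of RANAS factors on handwashing, not the effect of the intervention.

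The outcome is measured before the intervention. The Synopsis (Measurements and Procedures) states: "Endpoints of Modules 1-3 will be assessed at baseline, at follow-up and endline of the cRCT". Baseline handwashing is nevertheless not named as a covariate for the intervention effect. Nor are country or the variables used in the randomisation. Section 4 describes that randomisation as covariate-constrained and stratified, section 4.3 as stratified block.

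**The concern.** Covariates reach the adjusted model by two routes: as known confounders, which are not named, and as variables found to be imbalanced. The second route selects on the wrong property. Adjustment gains precision from a covariate's link with the outcome. A chance difference between arms is no evidence of such a link, and by itself it only adds variance to the estimated effect.

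The design sharpens the problem. Constrained or stratified randomisation exists to balance characteristics thought to matter. Those variables will then tend not to look imbalanced, so the second route will tend to leave them out, although an analysis that respects the design would include them.

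At stake is the value of the adjusted result as support for the primary one. It may give up precision that is available at no extra data cost, and it uses school-level degrees of freedom, of which there are few. Its content also depends on a judgement made after allocation, by a statistician who, according to section 4.3, cannot be blinded.

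**Working it through.** **Inputs from the documents.** 13 schools per arm, 50 students per school, 20% against 45%, ICC 0.2 (section 6.2); error rates from "aiming for a power of 80% at the 95% confidence level". Sidedness is not written. Two-sided 0.05 is assumed, which fits the non-directional hypothesis in section 6.1.1. The Synopsis gives 26 schools in total (13 per arm). Section 4 gives 26 per country (26 per arm over both countries). Both are shown.

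**The plan's own figure.** The comparison of 20% with 45% needs 54 students per arm without clustering. The design effect is 1 + 49 × 0.2 = 10.8, so 54 × 10.8 / 50 = 11.66 schools, rounded up to 12. With a t reference on 2k − 2 degrees of freedom, power is 79.7% at 12 schools per arm and 83.0% at 13. The stated 13 per arm is reproduced, and it does not depend on the adjusted model.

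**How often imbalance arises by chance.** Under simple randomisation, the standardised difference of a school-level covariate is roughly normal with variance 2/k.

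| Schools per arm | SD of difference | P(above 0.1) | P(above 0.25) | P(above 0.5) |
|---|---|---|---|---|
| 13 | √(2/13) = 0.392 | 80% | 52% | 20% |
| 26 | √(2/26) = 0.277 | 72% | 37% | 7% |

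At 13 per arm, a truly prognostic covariate therefore goes unflagged 20%, 48% or 80% of the time, depending on a threshold that the plan does not state.

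**Cost of one irrelevant covariate.** Adjusting for a covariate with standardised difference d multiplies the variance by about 1 + d²/4. The standard error (SE) rises by 0.8% at d = 0.25, 3.1% at d = 0.5 and 11.8% at d = 1. Each cost is small, but they add up with 26 schools.

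**Simulation of the rule.** Assumptions not in the documents: school-level linear regression with outcome SD 1, simple allocation, one prognostic covariate (baseline handwashing) with correlation 0.6, and 3, 5 or 10 candidates of which the rest are irrelevant. Thresholds are 0.25 and 0.5 SD. The entries are mean SEs of the arm effect.

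| Analysis | 13 per arm | 26 per arm |
|---|---|---|
| Unadjusted | 0.39 | 0.28 |
| Imbalance selection only | 0.37–0.43 | 0.26–0.28 |
| Baseline handwashing always in, others by imbalance | 0.33–0.39 | 0.22–0.24 |
| Baseline handwashing alone, fixed in advance | 0.32 | 0.22 |

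Two rows can be checked by hand. Unadjusted: √(2/13) = 0.392 and √(2/26) = 0.277. Fixed covariate: √(1 − 0.6²) = 0.8, so 0.8 × 0.392 = 0.314 and 0.8 × 0.277 = 0.222, before a small loss for the fitted term.

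**Variables balanced by design.** A second simulation used 13 schools per arm, proportion-scale ICC 0.2, empirical logits, correlation 0.5 and five irrelevant candidates. The allocation was drawn from the 10% best balanced on the prognostic covariate. That covariate was flagged in essentially no run. Power was 75–79% under the imbalance rule, against 91% with the covariate fixed in advance.

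**Type I error.** In the second simulation, under simple allocation, the imbalance rule rejected a true null in 3.6–4.1% of runs. This is slightly conservative.

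**The case against.** The strongest reply is that imbalance is only half of the rule. Known confounders enter whether or not they are imbalanced, and baseline handwashing could be counted among them. The word predictors in section 6.3.1.2 may also confine the second route to variables linked with the outcome. This stands as far as it goes. A reader might infer that the rule usually skips the covariates that matter and picks the costliest ones. The documents do not support that, because the confounders and the threshold are both unstated.

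A reader might also infer that adjustment under this rule makes the SE about 10% larger (0.43 / 0.39 = 1.10). That needs ten mostly irrelevant candidates and no contribution from the known-confounder route. With three candidates the SE is 0.37 to 0.39, no worse than unadjusted; with five it is about 0.39 to 0.40. If baseline handwashing always enters, it is at most 0.39. At 26 schools per arm the loss against no adjustment is at most 2%.

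Nor is the trial's main result at risk. The primary model is fixed and unadjusted, so its type I error and the sample size do not depend on this rule. Judging imbalance by clinical importance is also better than testing it for significance.

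The reply does not rescue the imbalance clause. Even with baseline handwashing always included, adding flagged variables among ten candidates gives an SE of 0.385 (threshold 0.25 SD) or 0.36 (0.5 SD), against 0.32 with that covariate alone. And the documents do not say that baseline handwashing is a known confounder of the intervention effect.

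**Conclusion.** The concern holds for the secondary adjusted analysis. Its covariates are not fixed, and part of them would be chosen on a property unrelated to prognosis. In every setting simulated with a correlation of 0.6, one prognostic covariate fixed in advance gave a smaller mean SE than the imbalance rule. At 13 schools per arm the gain over no adjustment is about 18% (0.32 / 0.39 = 0.82). Under the rule the result ranges from about 15% better than unadjusted (0.33 / 0.39) to about 10% worse (0.43 / 0.39), depending on choices that the plan leaves open.

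The sizes rest on an assumed correlation of 0.6, 3 to 10 candidates and simple allocation. They shrink if 26 schools per country is the intended number. They come from a linear model at school level. In the planned logistic mixed model, adjusted and unadjusted odds ratios are different conditional quantities, so their SEs are not strictly comparable. The absence of a list and threshold is certain; the exact loss is not. The change should be made, but nothing in the primary inference hangs on it.

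**What to change.** In section 6.3.1.2 and in the Synopsis, replace the imbalance clause, and the unnamed confounders, with one short list entered regardless of observed balance:

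- baseline handwashing before eating: the school proportion and, where available, the pupil's own baseline response;
- country;
- the variables used to stratify or constrain the randomisation;
- sex;
- age or grade.

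State that baseline imbalance is described only and does not alter the model. Keep the list short, because each school-level term uses one of few degrees of freedom.

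Two passages must be settled first: sections 4 and 4.3 on the type of randomisation, with its variables named, and section 4 against the Synopsis on 26 schools per country or in total.

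The cost is a change of wording before endline data are seen; baseline handwashing is already collected. The downside is that a chance imbalance in an unlisted variable is discussed and not modelled.
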